## Procedure

Inclusion will be open for 18 months, planned from September 2024. Participants will be recruited from outpatient specialised mental health care facilities in the Western Norway Regional Health Authority and South-Eastern Norway Regional Health Authority. After recruitment, each participant will undergo an assessment for eligibility where inclusion and exclusion criteria are evaluated. If eligible, participants are asked to sign a written informed consent to participation before enrolment in the study. Participants will receive access to the program after consent has been given, using level four secure login, for example BankID or Buypass ID. Participants receive a short tutorial of the program by their eTherapist. When logged in the first time, and as a mandatory task before given access to the program, participants are asked to revise their consent in regards to their unidentifiable data being used in research. Participants can at any time during treatment withdraw their consent. In this case they will be able to continue treatment, but their user data will not be exported for research purposes. Demographic variables and questionnaires will be given as a mandatory task before the first module and are registered directly in the program. The program is set to take 12 weeks to finish.

The main form of contact between participant and eTherapist will be via asynchronous messages. If asked for by the participant, or evaluated as necessary by the eTherapist there will be contact via phone or face-to-face. If a participant fails to log in for more than seven days the eTherapist will make contact via phone or SMS giving them an appointment to evaluate further progress. If a patient drops out of the program the eTherapists are to use their local procedures to how this person is taken care of, see also section for Ethical Considerations.

After 12 weeks the participants will be given a concluding session face-to-face where the next step is decided: End treatment, further treatment within the specialist mental health

care services or referred to a different treatment option. Regardless of this the participants will have access to the treatment program, without therapist contact, for six months after completion.

Participants will be asked to take part in a voluntary interview with a research fellow in the project. After six and 12 months, participants will be notified via SMS asking them to fill out self-report questionnaires. They will be given two reminders via SMS if they do not respond. If they do not fill in the forms after the two reminders they will be regarded as lost to follow up.

## **Project management**

The project has academic and clinical collaborators. For a description of implementation of the project, see the complete Project Directive for Implementation in Appendix C.

## **Ethical considerations**

### **The therapist's level of competence**

The therapists giving the treatment program are clinical psychologists or have at least a bachelor degree in health (Nurses, social workers and occupational therapists). In addition all therapists are trained in eTreatment in general, this program specifically and are given weekly or bi-weekly guidance on eTherapy within their workplace and by the project group.

### **Monitoring suicidal risk or behaviour**

Participants will each week answer question 10 (suicidal ideations) of the Montgomery and Åsberg Depression Rating Scale (MADRS; Malt, 2016; Montgomery & Asberg 1979) and the total CORE-10. Both of these questionnaires have a cut-off for risk which, if surpassed, leads to an automatic text message and e-mail to the participants' eTherapist and local program supervisor. The eTherapist, or the program supervisor contacts the participant and follows their local procedure on assessing suicidal risk and take precautionary measures as deemed necessary. This will include a face-to-face evaluation and assessment of the level of care needed. The process and conclusion will be documented in the participants electronic journal (EPJ).

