### **Knowledge gap**

Current treatment is often targeting specific disorders without explicitly addressing RTW challenges and the coping strategies needed for RTW in the treatment packages. There is a need for studies that examine the potential contribution of interventions that integrate a systematic focus on work-related issues in a comprehensive therapeutic framework.

To the best of our knowledge there has been little or no research on a transdiagnostic cognitive behavioural therapy approach to work-focused therapy, nor a digital version of work-focused therapy for CMD targeting out-patients. The individual evidence of transdiagnostic ICBT and face-to-face W-CBT is compelling. An effective combination of these would be an important development towards increased availability of work-focused therapy. A small feasibility study on the program “eBehandling - Health and Work” performed by the authors have shown that the combination seems feasible, but there is a need for a larger scale study to determine the utility and use of the program for wider implementation. The potential contribution of this study is to explore the utility and feasibility of a broadly applicable treatment program for emotional disorders, that is built around RTW. There is also a need for more knowledge about the potential negative effects, as these have earlier not been adequately assessed in treatment research.

The single arm trial design aims to obtain preliminary results on treatment effects on RTW and clinical symptoms, as well as data on use and utility of the ICBT program as experienced by the patients. It is also the case that relatively little is known about what works

and for whom in the field of work-focused ICBT. This study aims to address this knowledge gap by exploring how common clinical and demographic factors impact treatment response.

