## **Hypotheses of moderating and mediating effects and predictors of outcome**

**H4.** We expect a negative relationship between duration of baseline work absenteeism and degree of return to work at post. Baseline work absenteeism will moderate the relationship between treatment and return to work.

**H5a.** We expect treatment credibility at baseline to be predictive of treatment adherence.

**H5b.** We expect that treatment adherence will be a mediator between treatment credibility and treatment outcome.

**H6.** We expect changes on the Return to Work Self-Efficacy Scale to predict the degree of absenteeism post treatment.

**H7.** We expect change on the Return to Work Self-Efficacy Scale to be a mediator between baseline absenteeism and return to work post-treatment.

**H8.** We expect higher depression scores (PHQ-9/CORE-OM score) to be a moderator between treatment credibility and treatment outcome and adherence.

**H9.** We expect that fewer than 10% of participants experience negative effects caused by participation, as measured by the Negative Effects Questionnaire (NEQ).

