most and least frequently, and how the therapist guidance is used. Further we also will analyse how long each session lasts and what system and platform they use. Each eBehandling location will also maintain local statistics on the number of assessment interviews, participants included and excluded to assess acceptance in the patient population and hospital setting. This data collection will be recorded by on-site super users. Efforts will be taken to ensure that this registration is implemented in the Youwell platform.

**Qualitative in-depth interviews.** Two months after completion of the program, a subset of participants will be invited to an in-depth interview (See Appendix A for the complete Interview Guide). We will use purposive sampling to select participants who represent a diverse range of demographics (age, gender) and outcomes (treatment responders and non-responders). Care will be taken to include participants from different treatment sites. We aim to recruit a total of 20 participants for the qualitative interviews, likely ensuring richly-textured information on a broad array of participant experiences.

The interview has a semi-structured design with six questions and related probes (See Appendix A for the complete Interview Guide). The interviews will be conducted by research fellow [name]. The interviews will focus on the participants' experience of the feasibility of the intervention, including aspects of the treatment viewed as helpful and less helpful. All interviews will be audio recorded and transcribed verbatim.

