## Statistical analyses

**Quantitative analyses.** In order to identify factors associated with treatment success and outcomes, hierarchical linear mixed modelling analyses (HLM, “multilevel”) will be conducted. In longitudinal HLM, measurement occasions (time) are nested within participants. Fixed effects are average (main) effects, and do not vary across subjects. Random effects vary across subjects and/or measurement occasions (e.g., a random intercept model vs a random intercept, random slope model). In these models, data may be missing at random and at different occasions for different subjects (Tasca & Gallop 2009). The models will be checked if they fulfil the model assumptions of normality of residuals, linearity and homoscedasticity. The dependent variables are sick leave, work related self-efficacy (as measured by RTWSE-11), depression severity (PHQ-9), anxiety (GAD-7), well-being, symptoms, risk and function (CORE-OM) and impairment in functioning (WSAS). The predictors are: Treatment (time), duration of sick-leave prior to treatment, treatment credibility, work related self-efficacy, depression severity and adherence. Comparisons are modelled through main effect and interaction effect analysis (e.g. Time x “Baseline work absenteeism” interaction). Predictors will be centred using grand mean centering. T-values and degrees of freedom will be estimated using “Satterwaite” correction (Luke 2017). The effects sizes will be converted from *t*-values and degrees of freedom to Cohen’s *d* using the R-package “effectsize”. Estimating indirect effects (mediation), we will apply “causal mediation analysis” (CMA), that is a method to split a total effect of an independent predictor (X) into a direct (C) and indirect effect (M). The indirect effect is transmitted through a mediator to the outcome. CMA will be conducted under the assumption of sequential ignorability. The X will be measured at baseline, the M at intermediate treatment, and the outcome(s) at post-treatment (Zhang et al. 2016). See Figure 2 below for a tentative model.

[figure not shown]

Figure 2. Model of mediation.

Corrections for multiple analyses will be done by using Jaccard's correction (Jaccard, 1998) to decrease risk of Type I error when applying several statistical tests.

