## **Data and privacy protection**

The Youwell platform and concerns of health information have been processed and approved for clinical use via the Western Norway Regional Health Authority based on a risk and vulnerability analysis and Data Protection Impact Assessment (DPIA, See Appendix D for the DPIA). The process in regard to research within a clinical setting is started within Helse Vest and is scheduled to be finished before July 2024. Regarding the specific considerations concerning data extraction this has been evaluated together with a data protection officer (PVO) using a DPIA. Data will be extracted by the PhD candidate using a researcher's access. This grants access to all the reports on self-evaluation and program usage, bar free text answers. It does not give access to the personal profiles of the participants, nor their activities in the program. The export is further limited by default to exclude any who have withdrawn their consent during treatment. Data will be encrypted and saved on secure storage area from Helse Vest IKT and on safe storage (SAFE) at UiB.

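### The harm result rests on the NEQ self-report alone, and no stated route brings the outcome of suicidal-risk alerts or serious events into the research data

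*Protocol*

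**What the plan says.** **Harm as a trial question.** The Knowledge gap section gives harm as a reason for the study: "There is also a need for more knowledge about the potential negative effects, as these have earlier not been adequately assessed in treatment research". Research question 4 asks which negative effects participants report and how often. H9 reads: "We expect that fewer than 10% of participants experience negative effects caused by participation, as measured by the Negative Effects Questionnaire (NEQ". Measures describes the NEQ as a 20-item self-report form about events during treatment.

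**Risk monitoring.** Under Monitoring suicidal risk or behaviour: "Participants will each week answer question 10 (suicidal ideations" of the MADRS, together with the whole CORE-10. Then: "Both of these questionnaires have a cut-off for risk which, if surpassed, leads to an automatic text message and e-mail" to the eTherapist and the local program supervisor. Local procedure follows, including a face-to-face evaluation. On the record of this: "The process and conclusion will be documented in the participants electronic journal (EPJ".

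**What reaches the researchers.** Data and privacy protection says of the researcher's access: "This grants access to all the reports on self-evaluation and program usage, bar free text answers". Personal profiles and activities in the program are excluded. Under Measures, each site will "maintain local statistics on the number of assessment interviews, participants included and excluded to assess acceptance".

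**What is analysed.** The dependent variables in Statistical analyses are sick leave, RTWSE-11, PHQ-9, GAD-7, and "well-being, symptoms, risk and function (CORE-OM) and impairment in functioning (WSAS". CORE-10 is listed as a secondary outcome in Measures but is not among these variables. MADRS question 10 is in neither list.

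**The concern.** The most serious signals in this trial follow a different path from its harm measure. The NEQ is a research form. The handling of a risk alert is a clinical process recorded in the clinical file. The protocol does not say how the two meet.

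This matters because the NEQ depends on the participant still answering. Someone whose condition worsens, or who is moved to other care, is plausibly among those least likely to complete it. The protocol plans for 30% drop-out (Power analyses), offers drop-outs other treatment (In the case of participant drop out), and treats those who do not answer the follow-up reminders as lost (Procedure). H9 could then be reported as met while confirmed risk events or escalations among non-responders remain uncounted. With no control arm, and with wider implementation as the stated purpose, the safety description should cover everyone who started.

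**Working it through.** The plan gives no figure for this point, so there is none to reproduce. The check is a trace of each source of harm information, followed by simple arithmetic on missing NEQ forms.

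**Step 1. Trace of each source**

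| Source | Reaches the research data? | Stated use |
|---|---|---|
| NEQ | Yes, self-report | Research question 4 and H9 |
| CORE-OM risk | Yes, self-report | Dependent variable |
| Weekly CORE-10 | Appears so, self-report | Secondary outcome; not a dependent variable |
| Weekly MADRS question 10 | Appears so, self-report | In neither list |
| What followed an alert | No route stated | None stated |
| Suicide attempt, transfer of care, death | No research form named | None stated |

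The last two rows are the gap. The researcher's export does not name the clinical record as a source, and the site statistics count interviews, inclusions and exclusions.

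**Step 2. One participant followed through the text**

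A participant crosses a cut-off in week 5, is evaluated, moves to other care and completes no NEQ. The weekly scores up to that point appear exportable, and the system data show where the participant stopped. The evaluation, its conclusion and any serious event do not reach the research data by any stated route. H9 does not count this person.

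**Step 3. How much of the sample the NEQ may miss**

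Inputs from Power analyses: N = 390 and 30% drop-out. Assumption: drop-out means no NEQ. The protocol does not say at which occasions the NEQ is given; if it is also given at six weeks, fewer would lack one.

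- Without a NEQ: 390 × 0.30 = 117. With a NEQ: 390 − 117 = 273.
- Largest count under 10% of 273: ceil(27.3) − 1 = 27, and 27/273 = 9.9%.
- Largest count under 10% of 390: ceil(39.0) − 1 = 38. The limit is reached at 39.
- With k NEQ cases among 273, the limit over all 390 is reached when 39 − k of the 117 are also affected:

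| k of 273 | Share | Needed among 117 | Share |
|---|---|---|---|
| 27 | 9.9% | 12 | 10.3% |
| 20 | 7.3% | 19 | 16.2% |
| 14 | 5.1% | 25 | 21.4% |

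This concerns negative effects as H9 defines them, not alerts. It shows how far the H9 result depends on people who may not have answered.

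**Step 4. Serious events**

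The documents give no rate. Over an assumed range of 0.5%, 1%, 2% and 5%, the expected numbers among 390 are 390 × rate = 1.95, 3.9, 7.8 and 19.5, or about 2 to 20 people. If events were collected for all 390 and none occurred, the exact two-sided 95% upper bound would be 1 − 0.025^(1/390) = 0.94%. Without collection, the trial can make no such statement.

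**The case against.** Several stronger readings are tempting, and the documents do not support them.

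- **That alerts are recorded nowhere but in the clinical file.** The protocol says where the process and conclusion are documented; it does not exclude other records. The scores that trigger an alert are self-report data and appear exportable, so crossings can be counted.
- **That risk goes unanalysed.** CORE-OM risk is a dependent variable and CORE-10 is a secondary outcome. The list in Statistical analyses describes the mixed models, and a statistical analysis plan not shown may describe the weekly scores.
- **That such a participant leaves no trace.** There is a six-week assessment, the models allow partial data, and the system records where people stop.
- **That the number missed can be taken from the 2.9% average deterioration in the review abstract in the reference list.** That figure is deterioration in other programs, not a rate of risk events.
- **That every alert is a harm of the program.** H9 concerns effects caused by participation. An alert is a screening result in specialist outpatients, and a single arm cannot attribute it to treatment.

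These objections stand. It is also true that Appendix C (the implementation directive) and Appendix D (the data protection assessment) are not shown and could hold event reporting.

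They do not close the gap. An analysis plan can add a table of weekly scores, but it cannot analyse alert outcomes that were never collected. A mean change in CORE-OM risk is not a count of events and says nothing of what followed an alert.

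**Conclusion.** The point holds in a limited form. H9 has one named measure, the NEQ; no section shown routes alert outcomes or serious events into the research data; and the weekly CORE-10 and MADRS question 10 are not among the dependent variables. The harm result can therefore understate harm among those who stop before the NEQ.

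The size is not known. On the plan's own figures, about 117 of 390 could lack a NEQ, assuming that drop-out means no NEQ. The number of serious events among them cannot be derived from the documents; the range in step 4 is an assumption. A reader might infer that harm is certain to be understated. That would require participants without a NEQ to fare worse, which is plausible but not shown.

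The clinical safety process itself is described. The shortcoming is in what the trial can report.

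**What to change.** 1. **Use the scores already collected.** For all who started, report the number and share crossing the platform's existing alert cut-offs on CORE-10 and MADRS question 10. Also report CORE-10 deterioration at the last available week, using a reliable-change threshold fixed in advance so that small fluctuations are not counted.
2. **Collect what followed.** Have sites record, per participant under the study code, each alert, whether the face-to-face evaluation took place, any transfer to a higher level of care, and any suicide attempt or death. Report these counts beside the NEQ, with all who started as the denominator.
3. **Keep the claims apart.** Present these as safety events regardless of cause, separate from the H9 test. State the number without a NEQ next to the H9 result.

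The cost is a participant-level addition to site statistics that are now described as counts, and a check of the data protection assessment, the data-access limits and the consent text, because outcomes would be drawn from the clinical record. The reported safety figure may be less favourable. No new assessment of participants is needed, and no clinical rule or cut-off changes.

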### **Transdiagnostic treatment for specific or comorbid diagnosis**

There is compelling evidence that transdiagnostic treatment protocols are effective in influencing the underlying mechanisms of CMDs through the reduction of fear and avoidance of, and increasing acceptance of emotions, physical sensations and establishing alternative, more adaptive behaviours (González-Robles et al. 2020, Schaeuffele et al. 2021). This is found in both face-to-face therapy and ICBT. As we have developed the treatment in the current study on these established principles we see no imminent increased risk of reduced effect of the treatment on CMDs in this study.

## **In the case of participant drop out**

If a patient drops out of treatment, or together with their eTherapist concludes that the treatment program of this study is not suitable, they will be given access to other, suitable treatment either via “eBehandling” or face-to-face treatment at their local District Psychiatric Center. (DPS).

## **Data and privacy protection**

The Youwell platform and concerns of health information have been processed and approved for clinical use via the Western Norway Regional Health Authority based on a risk and vulnerability analysis and Data Protection Impact Assessment (DPIA, See Appendix D for the DPIA). The process in regard to research within a clinical setting is started within Helse Vest and is scheduled to be finished before July 2024. Regarding the specific considerations concerning data extraction this has been evaluated together with a data protection officer (PVO) using a DPIA. Data will be extracted by the PhD candidate using a researcher's access. This grants access to all the reports on self-evaluation and program usage, bar free text answers. It does not give access to the personal profiles of the participants, nor their activities in the program. The export is further limited by default to exclude any who have withdrawn their consent during treatment. Data will be encrypted and saved on secure storage area from Helse Vest IKT and on safe storage (SAFE) at UiB.

## **Financing sources**

The study is currently funded by Solli DPS and previously assigned strategic funding from the Western Norwegian Regional Health Authority. We will apply for funding from the Western Norwegian Regional Health Authority.

## **Conflicts of interest**

No conflicts of interest are stated by the research project group.

## **Publications and communication of results**

The results will be published in high impact, international open access peer review journals. The titles of the planned papers are:

*Paper I:* The use and utility of a new digital transdiagnostic work-focused cognitive behaviour therapy program for patients on sick leave in specialised mental health care.

*Paper II:* Mediators and moderators for treatment utility of a digital work-focused therapy program.

*Paper III:* Participants experience with digital work-focused therapy – a qualitative study.

The results will be presented at international and national conferences. The PhD candidate in the study will contribute with popular science articles for user groups and the general population. Speeches and lectures will be given to relevant groups such as health care practitioners in specialised mental health care, municipal health care practitioners and relevant user organisations.

